4.4.3.2. Hematologic Endpoints

All hematologic endpoints indicated below will be based on subjects in the TP and summary tables will be presented by group.

- **Weighted average of the following at Month 6, 12, 18 and 24:**
 - non-transfused total Hb
 - HbS percentage of non-transfused total Hb
 - HbS percentage of non-transfused total Hb $\leq 70\%$, $\leq 60\%$, $\leq 50\%$
 - HbA^{T87Q} percentage of non-transfused total Hb
 - non-HbS percentage of non-transfused total Hb

Descriptive summary statistics or frequency distribution of the weighted average of the endpoints above at Month 6, 12, 18 and 24 will be provided. Data starting ≥ 60 days after the last pRBC transfusion will be utilized. The weighted average will be based on the assessments obtained up to an approximately 6-month period and can be calculated in a similar way as the weighted total Hb in the Globin Response in [Section 4.4.2](#). For example, for the weighted average at Month 6, all assessments post-drug product infusion up to Month 6 Visit will be used; for the weighted average at Month 12, all assessments obtained between Month 6 Visit and Month 12 Visit will be utilized for the calculation.

- **Assessment of the following over time:**
 - non-transfused total Hb
 - HbS percentage of non-transfused total Hb
 - HbA^{T87Q} percentage of non-transfused total Hb
 - non-HbS percentage of non-transfused total Hb

Descriptive summary statistics will be provided for the endpoints above over time per SOE. If there are multiple assessments within the same SOE time window, the average values will be presented in the tables. Change from baseline in non-transfused total Hb will also be presented, where baseline total Hb (as defined in [Section 1.2.6.2](#)) will serve as the baseline for non-transfused total Hb.

- **Hemolysis markers, markers of iron stores, and markers for stress erythropoiesis**

Descriptive summary statistics will be provided for these biomarkers over time and change from baseline will also be presented. Baseline is defined the first assessment on or after Informed Consent but before initiation of stem cell collection.

- **Change from baseline in annualized frequency and volume of pRBC transfusions between 6 months and 24 months after drug product infusion**

Absolute and percentage change from baseline in annualized frequency and volume (in mL/kg) of pRBC transfusions between 6 months (i.e., 183 days) to 24 months post-drug product infusion will be presented for Group C subjects in summary table. Baseline is defined as annualized frequency and volume of pRBC transfusions in the 24 months prior to Informed Consent and it is

only collected for Group C subjects. The final analysis will be based on Group C subjects in the TP. The summary statistics may be repeated for TPVOE subjects in Group C.

At the time of analysis, the day of the last available follow-up to the Month 24 visit (inclusive) will be used. For example, if a subject has only 700 days of follow-up post-drug product infusion, the annualized frequency or volume of pRBC will be adjusted by 700 days. Using volume as an example, it will be defined as:

$$\frac{\text{Total volume (mL/kg) received during 183 to 700 days post drug product infusion}}{(700 - 183 + 1)/365.25}$$

For volume of pRBC (in mL/kg) calculation, the weight (in kg) at or closest (in absolute value) to the date of the transfusion will be used. For example, if there are 2 weight assessments, one is 45 kg and 30 days before the transfusion, the other is 43 kg and 5 days after the transfusion, and no other weight assessments that are closer to the transfusion have been recorded, then 43 kg will be used for the calculation. The imputation rules for partial information of pRBC transfusion can be found in [Appendix 6.1, Table 11](#). The weight (in kg) at screening will be used for the calculation in annualized pRBC volume (in mL/kg) at baseline.

Change from baseline in annualized volume of pRBC transfusion will be presented in the following categories:

- Increased
- No change
- >0 and <50% reduction
- ≥50% reduction
- ≥60% reduction
- ≥75% reduction
- ≥90% reduction
- 100% reduction

The pRBC transfusions in Groups A and B subjects during the study will be presented in the listing without change from baseline calculation.

4.4.3.3. Clinical and Disease Evaluation Endpoints

The following endpoint will be only for subjects who have at least 4 protocol VOEs in the 24 months prior to Informed Consent (TPVOE).

- **Change in the annualized number of VOEs in the 24 months post-drug product infusion compared to the 24 months prior to Informed Consent**

The formula for annualized number of VOE on or post-drug product infusion is:

$$\frac{\text{Number of VOEs started on or post drug product infusion}}{(\text{Number of days post drug product infusion})/365.25}$$

If a VOE starts before drug product infusion but ends after drug product infusion, this event will not be included in annualized number of VOE post-drug product infusion calculation.

The number of adjudicated VOEs for each subject will be based on the number of unique VOE ID. The number of protocol or investigator VOEs for each subject will be based on the number of unique CRF page numbers.

Descriptive summary statistics of annualized number of VOEs at baseline, in 24 months post-drug product infusion, absolute and percentage change in the annualized number of VOEs compared to the 24 months prior to Informed Consent will be provided. Change from baseline in annualized number of VOE will be also presented in the following categories:

- Increased
- No change
- >0 and $<25\%$ reduction
- $\geq 25\%$ and $<50\%$ reduction
- $\geq 50\%$ reduction
- $\geq 60\%$ reduction
- $\geq 75\%$ reduction
- $\geq 90\%$ reduction
- 100% reduction

Summary statistics for annualized number and change from baseline for VOEs between 6 months and 18 months, and between 6 months and 24 months after drug product infusion may also be presented.

The following endpoints will be only for Group C subjects who have at least 4 protocol VOEs in the 24 months prior to Informed Consent (TPVOE).

- **sVOE-CR24**

The number and percentage of subjects with sVOE-CR24 will be presented for Group C subjects with a 2-sided 95% CI using the Clopper-Pearson method.

Responders of sVOE-CR24 are subjects who do not have any adjudicated sVOE in 6 to 24 months post-drug product infusion (i.e., 183 days post-drug product infusion to 731 days post-drug product infusion or the Month 24 visit, whichever is earlier).

Non-Responders of sVOE-CR24 are subjects who meet either of the following situations:

- Have ≥ 1 adjudicated sVOE in 6 to 24 months post-drug product infusion. If a subject has an adjudicated sVOE that occurs before 183 days post-drug product infusion but ends after 183 days post-drug product infusion, the subject is considered as a non-responder.
- Discontinued before completing the study.

- **VOE-CR24**

VOE-CR24 will be derived in a similar way as sVOE-CR24. The number and percentage of subjects with VOE-CR24 will be presented for Group C subjects with a 2-sided 95% CI using the Clopper-Pearson method.

- **sVOE-75**

The number and percentage of subjects with sVOE-75 will be presented for Group C subjects with a 2-sided 95% CI using the Clopper-Pearson method.

Responders of sVOE-75 are subjects who have $\geq 75\%$ reduction from baseline in annualized number of adjudicated sVOE in up to 24 months post-drug product infusion.

Non-Responders of sVOE-75 are subjects who meet either of the following situations:

- Have $< 75\%$ reduction from baseline in annualized number of adjudicated sVOE in up to 24 months post-drug product infusion
- Discontinued before completing the study
- **Change in the annualized number of severe VOEs in the 24 months after drug product infusion compared to the 24 months prior to Informed Consent**

The annualized number of severe VOEs will be calculated in the same way as specified in annualized number of VOEs. For Group C subjects in the analysis population, a 1-sided 97.5% CI for the percentage change in the annualized number of sVOEs in the 24 months post-drug product infusion compared to the 24 months prior to Informed Consent will be provided. The detailed method for the 1-sided of 97.5% CI can be found in [Appendix 6.6](#).

4.4.3.4. SCD Burden and Chronic Complications Assessments

These SCD burden and chronic complications assessments will be presented in table summaries by group for all subjects in TP. All data will be presented in listings.

The absolute change at each visit from baseline will be summarized by group.

- **Change from baseline in renal function as measured by eGFR**
eGFR will be calculated by CKD-EPI formula for subjects ≥ 18 years old and Schwartz formula for subjects < 18 years old. The formulas can be found in [Appendix 6.5](#).
- **Change from baseline in cardiac-pulmonary function via TRJV, PFTs and LVEF**
 - TRJV over time for each subject will be classified into 2 categories: < 2.5 m/s versus ≥ 2.5 m/s. A shift table will be presented to show the change from baseline in TRJV classification. The change from baseline values in TRJV will be presented in a listing.
 - Pulmonary Function Tests (PFTs) over time of each subject will be classified into one of the five categories indicated in [Table 5](#). A shift table will be presented to show the change from baseline in PFTs classification.

Table 5. Classification of Pulmonary Function

Category of Pulmonary Function	% of Predicted value					FEV1/ FVC
	FEV1	FVC	TLC ^[1]	RV	DLco	
Normal	$\geq 80\%$	$\geq 80\%$	$\geq 80\%$	$\geq 80\%$	$\geq 80\%$	$\geq 70\%$
Obstructive	$< 80\%$	$< 80\%$	$\geq 80\%$	$\geq 80\%$	$\geq 80\%$	$< 70\%$
Restrictive: meet any situation below						

Category of Pulmonary Function	% of Predicted value					FEV1/ FVC
	FEV1	FVC	TLC ^[1]	RV	DLco	
situation 1	<80%	<80%	<80%		<80%	≥70%
situation 2	≥ 80%	≥ 80%	<80%	<80%	≥ 80%	≥70%
situation 3			<80%		<80%	
Mixed obstructive and restrictive			<80%	<80%	≥ 80%	<70%
Isolated low DLco	≥ 80%	≥ 80%	≥ 80%	≥ 80%	<80%	≥70%

DLco = carbon monoxide diffusing capacity; FEV1 = forced expiratory volume in 1 second; FVC = forced vital capacity; RV = respiratory volume; TLC = total lung capacity.

^[1] % predicted FEV1, FVC, RV and DLco are directly collected in the CRF. Predicted values for TLC are derived using the formulas below, and height (meter) is subject's height at the time of the assessment or at the closest time to the assessment.

Male (age 4 – 17 years): $10.0^{**}(-2.0018 + 2.5698 \cdot \log_{10}(\text{HEIGHT} \cdot 100)) / 1000$.

Male (age ≥18 years): $0.066^*(\text{HEIGHT} \cdot 100) - 5.79$

Female (age 4 – 17 years): $10.0^{**}(-2.033 + 2.5755 \cdot \log_{10}(\text{HEIGHT} \cdot 100)) / 1000$

Female (age ≥18 years): $0.0799^*(\text{HEIGHT} \cdot 100) - 7.08$

- LVEF over time and change from baseline will be presented in summary table and listing.
- **Change from baseline in meters walked during 6-minute walk test (6MWT)**

Descriptive statistics will be provided for the meters walked during 6MWT at baseline and visits post-drug product infusion. The absolute change from baseline will also be presented.

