4.2. Inclusion Criteria

Subjects must:

1. Be ≥ 12 and ≤ 50 years of age at time of consent.
2. Have a diagnosis of SCD, with either β^S/β^S or β^S/β^0 or β^S/β^+ genotype.
3. Previous Inclusion Criterion #3 is no longer applicable and has been replaced with Criterion #3.1.
 - 3.1. In the setting of appropriate supportive care measures (e.g., pain management plan) have experienced **at least 4 severe VOEs in the 24 months prior to informed consent as defined below**.

For the purposes of this study, a severe VOE is defined as an event with no medically determined cause other than a vaso-occlusion, requiring a ≥ 24 -hour hospital or emergency room (ER) observation unit visit or at least 2 visits to a day unit or ER over 72 hours with both visits requiring intravenous treatment. Exception: priapism does not require hospital admission but does require a medical facility visit; 4 priapism episodes that require a visit to a medical facility (without inpatient admission) are sufficient to meet criterion. Severe VOEs include:

- a. an episode of acute pain with no medically determined cause other than a VOE
- b. Acute chest syndrome (ACS), defined by an acute event with pneumonia-like symptoms (e.g., chest pain, fever [$> 38.5^{\circ}\text{C}$], tachypnea, wheezing or cough, or findings upon lung auscultation) and the presence of a new pulmonary infiltrate consistent with ACS and requiring oxygen treatment and/or blood transfusion.
- c. Acute hepatic sequestration, defined by a sudden increase in liver size associated with pain in the right upper quadrant, abnormal results of liver-function test not due to biliary tract disease, and reduction in Hb concentration by at least 2 g/dL below the baseline value
- d. Acute splenic sequestration, defined as sudden enlargement of the spleen and reduction in Hb concentration by at least 2 g/dL below the baseline value.
- e. Acute priapism: defined as a sustained, unwanted painful erection lasting more than 2 hours and requiring care at a medical facility (with or without hospitalization)

4. Previous Inclusion Criterion #4 is no longer applicable as of Protocol Amendment 8.0.

5. Have a Karnofsky performance status of ≥ 60 (≥ 16 years of age) or a Lansky performance status of ≥ 60 (< 16 years of age).
6. Previous Inclusion Criterion #6 is no longer applicable as of Protocol Amendment 8.0.

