5.5. Duration of Subject Participation

Time between Screening and drug product infusion will be variable and is estimated generally to be between 3 to 5 months (e.g., up to 3 months between Screening and Mobilization, followed by approximately 2 months before drug product infusion). Thereafter the subject is planned to remain on study for approximately 24 months. Eligible subjects are then expected to enroll in a separate long-term follow-up study until approximately 15 years post-drug product infusion. For subjects enrolled in Group B2 who opted to defer manufacture of drug product until Group C opened, the time between Screening and drug product infusion was extended as long as the subject continued to meet eligibility criteria.

If the subject is unable to undergo mobilization for drug product manufacture within approximately 3 months of the initiation of Screening, some assessments may need to be repeated to confirm continuing eligibility or to provide a reliable baseline prior to study procedures. In particular, physical exam, vital signs, performance status, HRQoL, echocardiogram, complete blood count, chemistry, urinalysis, and liver function tests, and for women of child-bearing potential, tests for pregnancy, must be performed within 3 months of proceeding to evaluation for mobilization. For subjects with exposure risks for HIV, HBV and HCV, these tests should also be repeated. Some of these assessments may be performed immediately prior to mobilization, as specified in the SOE. Where clinically and/or regionally indicated, other tests for infectious pathogens may be performed, as required by regional regulations or at physician discretion. Other blood tests, including those for immune subsets, hormonal or dyserythropoiesis testing only need to be repeated if more than 6 months have transpired, unless there is clinical concern due to an initial screening test (e.g., borderline thyroid function). Cerebral MRA/MRI and echocardiogram performed within 3 months of ICF and PFT results performed within 6 months of ICF may be used, unless there is clinical indication for repeat testing, or initial testing was borderline. The need for liver biopsy should be guided by MRI findings, as described in the protocol, unless a biopsy performed within 1 year of mobilization exhibited no evidence of fibrosis or hepatitis. Sickle cell disease genotyping, baseline VCN, baseline RCL and baseline β^{A-T87Q} -globin, once performed, do not have to be repeated.

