8.3. Subject Information and Informed Consent

After the study has been fully explained, written informed consent will be obtained from the subject or their legal representative prior to study participation. The method of obtaining and documenting the informed consent and the contents of the consent will comply with ICHGCP and all applicable regulatory requirement(s). If a subject is < 18 years of age at signing of informed consent/assent and turns 18 while on study, the subject should re-consent to the adult ICF at the next scheduled study visit.

Consent to this study indicates acknowledgement that follow-up is expected to last 15 years, with the first 2 years in this Study HGB-206 and 13 additional years in a long-term follow-up study. A brief summary of expected study procedures in the long-term follow-up study will be described in the Study HGB-206 consent so that the subject and/or their guardian or legal representative are aware of expectations in the long-term follow-up study. Consent for participation in the long-term follow-up study will be obtained at the time of enrollment in the long-term follow-up study.

If any concerning chromosomal abnormality or genetic mutation is identified prior to conditioning, and the subject intends to continue to stay on study (see [Section 6.2.11](#)), appropriate informed consent must be obtained after the results have been fully discussed.

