3.4. Baseline Definitions

For annualized number of endpoints, such as annualized number of VOEs, sVOEs, hospitalizations and pRBC transfusions, baseline will be defined as the annualized number of the corresponding endpoint in the 24 months before Informed Consent.

The definition of baseline total Hb for Globin Response derivation can be found in [Section 1.2.6.2](#). The baseline total Hb values are collected on the eCRF page of Baseline Hemoglobin. A subject will be considered as having no baseline Hb for Globin Response analysis if the subject has 1 or 0 qualifying Hb value from the Baseline Hemoglobin eCRF page.

For liver biopsy, liver MRI, Cardiac MRI, cerebral MRA/MRI, echocardiogram (including LVEF and TRJV), bone mineral density (BMD) and pulmonary function test (PFT), baseline will be defined as the first assessment during screening. If no records at screening, the last assessment prior to Informed Consent will be used.

Unless otherwise specified, for other efficacy, pharmacodynamic, and safety parameters, including shifts in key laboratory parameters, baseline will be defined as the first assessment during screening (which can be identified by the first record on or after date of Informed Consent Form [ICF], but before initiation of stem cell collection).

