Black	Male	> 79.6	$163 \times (\text{Serum Creatinine} \times 0.011312/0.9)^{-1.209} \times (0.993)^{\text{Age}}$
White or Other	Female	≤ 61.9	$144 \times (\text{Serum Creatinine} \times 0.011312/0.7)^{0.329} \times (0.993)^{\text{Age}}$
White or Other	Female	> 61.9	$144 \times (\text{Serum Creatinine} \times 0.011312/0.7)^{-1.209} \times (0.993)^{\text{Age}}$
White or Other	Male	≤ 79.6	$141 \times (\text{Serum Creatinine} \times 0.011312/0.9)^{-0.411} \times (0.993)^{\text{Age}}$
White or Other	Male	> 79.6	$141 \times (\text{Serum Creatinine} \times 0.011312/0.9)^{-1.209} \times (0.993)^{\text{Age}}$

Note: Conversion factor for serum creatinine umol/L $\times 0.011312 = \text{mg/dL}$

- For subjects < 18 years old, Bedside-Schwartz equation for eGFR ([Schwartz et al 2019; Schwartz and Work 2019](#)) as below

Conventional:

eGFR by Schwartz = $0.413 \times (\text{Height}/\text{Enzymatic serum creatinine})$, where:

- Enzymatic serum creatinine is reported in mg/dL (x.xx)
- Height is reported in cm (x.x)

SI:

eGFR by Schwartz = $0.413 \times (\text{Height}/\text{Enzymatic serum creatinine} \times 0.011312)$, where:

- Enzymatic serum creatinine is reported in umol/L (x.xx)
- Height is reported in cm (x.x)

6.6. Statistical Methods for Confidence Interval of Percentage of Reduction in Annualized sVOE or VOE

This section presents the 1-sided of 97.5% CI for percentage reduction in annualized sVOE in the 24 months after drug product infusion from baseline. The same statistical methods will be used for the corresponding annualized number of VOE analysis.

sVOE is count outcome. Hence, it is reasonable to assume the targeted patient sub-population has an underlying distribution Poisson (λ).

Assuming the sVOE data consist of $(N_{i0}, N_{i1}, T_{i0}, T_{i1})$, $i = 1, \dots, k$, where N_{i0} and T_{i0} are the number of sVOEs and follow-up time prior to Informed Consent, serving as baseline data, respectively, and N_{i1} and T_{i1} are the number of sVOEs and follow-up time after the treatment, respectively. In Study HGB-206, $T_{i0} = 2$ years for every subject.

We assume that given λ_{i0} and λ_{i1} , $N_{i0} \sim \text{Poisson}(\lambda_{i0}T_{i0})$, and $N_{i1} \sim \text{Poisson}(\lambda_{i1}T_{i1})$ are two conditionally independent variables with a common ratio

$$r = \frac{\lambda_{i1}}{\lambda_{i0}}, i = 1, \dots, k,$$

where r is the parameter of interest. Also note that sVOE reduction can be noted as θ , where $\theta = (1 - r)$.

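### The SAP switches the eGFR equation at age 18 without fixing the reference age, so change from baseline can include a false step in subjects who turn 18 on study

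*SAP*

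**What the plan says.** SAP 4.4.3.4 sets the rule: "eGFR will be calculated by CKD-EPI formula for subjects ≥ 18 years old and Schwartz formula for subjects < 18 years old". It then states: "The absolute change at each visit from baseline will be summarized by group". Appendix 6.5 gives the two equations and repeats the split ("For subjects < 18 years old, Bedside-Schwartz equation for eGFR"). Under SAP 3.4, for parameters without a special rule, "baseline will be defined as the first assessment during screening". No section says which age governs the choice, and no rule covers a subject who passes 18.

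The protocol makes such subjects likely. Inclusion criterion 1 is "Be ≥ 12 and ≤ 50 years of age at time of consent". Protocol 5.5 says the time from screening to infusion "is estimated generally to be between 3 to 5 months", and then: "Thereafter the subject is planned to remain on study for approximately 24 months". Protocol 8.3 has a re-consent rule for a minor who "turns 18 while on study".

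eGFR is also one of the laboratory tests in the CTCAE shift table (SAP Table 8, direction: decrease). The protocol itself, in exclusion criterion 12 and the laboratory table of 6.2.7, names only CKD-EPI, with no age split. SAP 5.1 nevertheless records no change from the protocol.

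**The concern.** A change from baseline is interpretable only if both values come from the same measure. Bedside-Schwartz and CKD-EPI give different values for the same person on the same day. If the equation changes between baseline and follow-up, the difference between equations is added to the reported change.

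The SAP accepts this principle elsewhere. For PROMIS (SAP 4.4.3.5), change from baseline is not calculated in domains that are not comparable across versions. eGFR has no equivalent rule.

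At stake are a named secondary efficacy endpoint and a safety shift table in subjects who have had busulfan and transplant. At many plausible creatinine values the step is upward, so it would look like renal improvement and could offset a real decline that arises after the 18th birthday.

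**Working it through.** **Who crosses 18.** Time from screening to Month 24 is 3 to 5 months plus 24 months, i.e. 27 to 29 months, or 2.25 to 2.42 years. 18 − 2.25 = 15.75 and 18 − 2.42 = 15.58. Subjects aged about 15.6 to under 18 at consent can therefore turn 18 by Month 24.

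**Which age the rule means.** The SAP does not say. Three features favour age at assessment:
- Where the SAP fixes age at consent, as in the subgroups of 3.8, it says so.
- Age is an input to CKD-EPI.
- The under-18/18-and-over split for the patient-reported forms follows age at the time of assessment (Protocol Table 5, footnote a).

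**Equations (Appendix 6.5, conventional units).** Scr is serum creatinine in mg/dL and height is in cm.
- Schwartz: 0.413 × height / Scr.
- CKD-EPI, female: C × (Scr/0.7)^a × 0.993^age, with C = 166 (Black) or 144 (White/Other), and a = −0.329 for Scr ≤ 0.70 or −1.209 above.
- CKD-EPI, male: C × (Scr/0.9)^a × 0.993^age, with C = 163 (Black) or 141 (White/Other), and a = −0.411 for Scr ≤ 0.90 or −1.209 above.

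The plan gives no eGFR change to reproduce. Its SI cut-points do check: 0.70/0.011312 = 61.9 and 0.90/0.011312 = 79.6 µmol/L, as printed.

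**Assumed inputs.** The documents give no creatinine or height for adolescents. I assumed age 18, unchanged creatinine and height, heights of 150–170 cm (female) and 160–180 cm (male), and creatinine from 0.3 to 1.0 mg/dL. 0.993^18 = 0.881.

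**Worked cases at 0.6 mg/dL.**
- Black male, 170 cm. Schwartz: 0.413 × 170/0.6 = 117.0. CKD-EPI: 163 × (0.6/0.9)^−0.411 × 0.881 = 163 × 1.181 × 0.881 = 169.7. Step: +52.7.
- Black female, 160 cm. Schwartz: 0.413 × 160/0.6 = 110.1. CKD-EPI: 166 × (0.6/0.7)^−0.329 × 0.881 = 166 × 1.052 × 0.881 = 153.9. Step: +43.8.
- White/Other male, 170 cm: 117.0 to 146.8, step +29.8.
- White/Other female, 160 cm: 110.1 to 133.5, step +23.4.

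**Range of the step over all heights (mL/min/1.73 m²).**

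| Creatinine (mg/dL) | Black | White/Other |
|---|---|---|
| 0.6–1.0 | +25 to +70 | +12 to +51 |
| 0.5 | +23 to +51 | +1 to +26 |
| 0.4 | 0 to +35 | −23 to +8 |
| 0.3 | −41 to +5 | −66 to −25 |

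The sign changes at about 0.33–0.40 (Black female), 0.29–0.35 (Black male), 0.41–0.49 (White/Other female) and 0.37–0.45 (White/Other male).

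**Could it hide a decline?** Take the Black male above and let creatinine rise from 0.6 to 0.9 after he turns 18. The mixed calculation gives 143.6 − 117.0 = +26.6. Schwartz throughout gives 78.0 − 117.0 = −39.0. The sign of the change is reversed.

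**Effect on the group mean.** SAP Table 1 shows 36 infused in Group C. One crosser at +50 moves the mean by 50/36 = 1.4; at +30, by 0.8.

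**With one equation per subject.** Schwartz throughout gives 0 at constant height and creatinine, and +3.4 for growth from 165 to 170 cm at 0.6 mg/dL (117.0 − 113.6). CKD-EPI throughout, age 16 to 18, gives −2.4 for the Black male at 0.6 mg/dL (172.1 to 169.7).

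**The case against.** The strongest reply is that the switch is inferred. The SAP names no reference date, and its subgroup definition is anchored at informed consent. If age at consent was intended for eGFR too, no subject changes equation. This stands as a limit on certainty. It does not remove the point, because the text as written lets a programmer apply age at each visit, and that is its more natural reading.

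Second, serum creatinine is already covered in SAP 4.6.3: summarised by visit, with its own CTCAE increase shift, a potentially-clinically-significant threshold and full listings. The shift tables take the most extreme abnormal value per interval, so a later upward step cannot erase an earlier low eGFR. This stands too: only a decline arising after the 18th birthday could be masked, and creatinine gives a second view of it.

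Third, a reader might infer that every crosser shows a false rise of tens. The documents do not support that: they give no creatinine values, and the step is small or negative at low creatinine.

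Fourth, a reader might infer that the adolescent mean moves by about +20, from 40% crossing (2.4 of 6 years, if consent ages were uniform from 12 to 18) at +50 each. The plan gives no age distribution and specifies the eGFR summary by study group in the transplant population, not for adolescents. The 40% would also apply only at Month 24.

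**Conclusion.** The concern holds as a flaw in the rule for a secondary, descriptive endpoint. SAP 4.4.3.4 and 6.5 leave the reference age open and allow two equations within one subject. On the natural reading, change in eGFR and the eGFR row of Table 8 can then record a false change at constant creatinine. The size, conditional on the assumed heights and age 18, is +23 to +70 mL/min/1.73 m² in Black subjects at 0.5–1.0 mg/dL and +12 to +51 in White/Other subjects at 0.6–1.0 mg/dL (+1 to +26 at 0.5). It fades or reverses below about 0.3–0.5 mg/dL.

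For an individual crosser this can exceed any plausible real change. For the Group C mean it is modest unless several subjects cross, and their number is not given. I did not compute CTCAE grade shifts, because the documents do not give the eGFR grade limits. No test or success criterion uses eGFR, so the trial's primary conclusion is unaffected.

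**What to change.** In SAP 4.4.3.4, Appendix 6.5 and the Table 8 eGFR shift, state that the equation is selected by the subject's age at baseline and kept at every visit for change from baseline and grade shift. Footnote subjects who turn 18 on study, and list the other equation's value for them as supportive. Their creatinine change is already in the planned summaries and listings and needs only a cross-reference.

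In SAP 5.1, record the age split as a departure from the protocol's CKD-EPI-only wording, or align the two documents.

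The cost is a few sentences and a small programming change, with no new data. The downside is that for crossers the paediatric equation runs past its stated age range by up to about two years. Using CKD-EPI throughout would also remove the step and match the protocol text, but it would apply the adult equation to all adolescents.

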- Change from baseline in markers of stress erythropoiesis, including erythropoietin and serum transferrin receptor

SCD Burden and Chronic Complications Assessments:

- Change from baseline in renal function as measured by eGFR
- Change from baseline in cardiac-pulmonary function via echocardiogram (tricuspid regurgitant jet velocity [TRJV], LVEF) and pulmonary function tests
- Change from baseline in meters walked during 6-minute walk test

Hospitalizations and Quality of Life:

- Change from baseline in annualized VOE-related hospital admissions and days
- Change from baseline in patient-reported quality of life, as measured by Patient Reported Outcomes Measurement Information System (PROMIS)

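### The SAP's adult formulas predict about 20% more total lung capacity for women than for men of the same height, the reverse of its own formulas for ages 4–17, so at least one adult equation or sex label is wrong.

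*SAP*

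**What the plan says.** Protocol section 2.2.1.3 lists change in cardiac-pulmonary function, including "pulmonary function tests", among the additional secondary efficacy endpoints. The schedules of events place the tests at Screening, Month 12 and Month 24.

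Under SAP section 4.4.3.4 each subject's results "will be classified into one of the five categories indicated in" Table 5. The analysis is then: "A shift table will be presented to show the change from baseline in PFTs classification".

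Table 5 cuts % predicted TLC at 80%. Every restrictive and mixed pattern needs TLC below 80%; normal, obstructive and isolated low DLco need 80% or more. According to footnote [1], the other four percentages (FEV1, FVC, RV, DLco) come from the CRF, but for TLC: "Predicted values for TLC are derived using the formulas below, and height (meter) is subject's height at the time of the assessment", or at the nearest available time.

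The footnote has four equations, by sex and age band. For adults:
- "Male (age ≥18 years): $0.066^*(\text{HEIGHT} \cdot 100) - 5.79"
- "Female (age ≥18 years): $0.0799^*(\text{HEIGHT} \cdot 100) - 7.08"

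For ages 4–17 it uses power functions of height. It cites no source for any of the four.

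**The concern.** The adult pair and the child pair disagree on which sex has the larger predicted lungs at a given height, and nothing in either document explains why the order should reverse at the eighteenth birthday. Because predicted TLC is computed by the SAP and not collected, no CRF value overrides a wrong equation.

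A predicted value that is too large makes % predicted TLC too small and pushes subjects under the 80% cut; one that is too small does the opposite. Both move subjects between Table 5 categories. The trial enrols from age 12 and follows subjects for 24 months, so some may also change equation between baseline and follow-up.

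**Working it through.** The SAP gives no worked TLC value, so there is no stated figure to reproduce. The inputs are the four equations in Table 5 footnote [1], with H the height in cm and results in litres:
- adult men: 0.066 × H − 5.79
- adult women: 0.0799 × H − 7.08
- boys 4–17: 10^(−2.0018 + 2.5698 × log10 H) / 1000
- girls 4–17: 10^(−2.033 + 2.5755 × log10 H) / 1000

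**Step 1: evaluate.** At 165 cm, men: 10.89 − 5.79 = 5.10 L; women: 13.18 − 7.08 = 6.10 L.

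| H (cm) | Men | Women | Women/men | Boys | Girls | Girls/boys |
|---|---|---|---|---|---|---|
| 150 | 4.11 | 4.91 | 1.193 | 3.89 | 3.73 | 0.958 |
| 160 | 4.77 | 5.70 | 1.196 | 4.60 | 4.40 | 0.958 |
| 165 | 5.10 | 6.10 | 1.197 | 4.97 | 4.77 | 0.958 |
| 170 | 5.43 | 6.50 | 1.198 | 5.37 | 5.15 | 0.958 |
| 180 | 6.09 | 7.30 | 1.199 | 6.22 | 5.96 | 0.959 |

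The adult lines cross at (7.08 − 5.79) / (0.0799 − 0.066) = 1.29 / 0.0139 = 92.8 cm, so the printed order holds at any plausible adult height.

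**Step 2: the step at age 18.** At 165 cm a girl's prediction goes from 4.77 to 6.10 L (+28%). If she was at 95%, she becomes 95 × 4.77 / 6.10 = 74% with unchanged lungs. A boy of that height goes from 4.97 to 5.10 L (under 3%).

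**Step 3: three explanations, at 165 cm.**
- *A. The adult lines are interchanged.* A woman's percentage is multiplied by 5.10 / 6.10 = 0.836, so she prints below 80% whenever her true value is below 80 / 0.836, about 96%. A man's is multiplied by 6.10 / 5.10 = 1.197, so he prints below 80% only if his true value is below 80 / 1.197, about 67%.
- *B. Only the female line is wrong, and women should sit about 4% below men as girls do below boys.* The prediction should be 5.10 × 0.958 = 4.89 L. The factor is 4.89 / 6.10 = 0.80, so nearly every woman with a true value below 100% prints below 80%. Men are unaffected.
- *C. Only the male line is wrong.* The men's prediction should be 6.10 / 0.958 = 6.37 L, and men print below 80% only below about 64%. Women are unaffected.

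Continuity at 18 (165 cm) helps to rank these. Under A, girls step 4.77 to 5.10 L (+7%) and boys 4.97 to 6.10 L (+23%). Under B, both step about 2.5%. Under C, both step 28%. So C, the only reading that spares women, fits the SAP's own child equations worst.

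**Step 4: from TLC to category.** TLC below 80% alone places nobody in a restrictive category. Situations 1 and 3 also need DLco below 80%; situation 2 and the mixed category also need RV below 80%. A woman whose only true abnormality is DLco below 80% moves from isolated low DLco to restrictive (situation 3) if her TLC prints falsely low. Such subjects can be in the trial, since only DLco below 50% is excluded. A woman with no other abnormality and a falsely low TLC fits none of the five categories.

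**The case against.** A reader might infer that the labels are certainly swapped, that restriction in men is therefore missed, and that the labels should simply be exchanged. The documents do not settle this. No passage says which adult line is wrong. The printed male line lies within about 4% of the boys' equation from 160 to 185 cm, so it could be right. Exchanging the labels would also move the discontinuity: a 170 cm boy turning 18 would go from 5.37 to 6.50 L (+21%), so 95% would become about 78%. The effect on men is conditional, and an exchange should wait for the source.

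A reader might also infer that the endpoint would measure the formula and not the lungs. That goes too far. For anyone adult throughout, essentially the same multiplier applies at baseline and follow-up, so relative change is preserved. What is distorted is category membership and movement across the 80% cut. The false fall needs a girl who turns 18 on study, and the documents do not say how many there are.

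Finally, the reach is limited. Protocol section 7.4.4.3 makes the endpoint descriptive. The test list in protocol section 6.2.25 names FVC, FEV1, RV and DLco but not TLC, so it is unclear how many subjects have a measured TLC at all.

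All of this stands as a limit on size. None of it explains an order that reverses at age 18.

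**Conclusion.** The point holds. As printed, adult women are predicted 19–20% more TLC than men of equal height from 150 to 180 cm, against about 4% less for girls than boys in the same footnote. At least one adult equation or sex label is wrong, and interchanged labels are the simplest explanation. This rests on the assumption that the order of the sexes should not reverse at 18, for which the SAP gives no justification.

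Women's % predicted TLC is very likely too low, by a factor of about 0.84 if the lines are interchanged and about 0.80 if only the female line is wrong. Men's is too high, by about 1.20, only if the lines are interchanged (or by somewhat more if the male line alone is wrong). The number of subjects who would change category cannot be derived from the documents. The primary and both key secondary endpoints do not use TLC and are unaffected.

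**What to change.** In SAP Table 5 footnote [1]:

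1. Verify both adult equations against their source and cite it. Correct the sex labels or coefficients accordingly, exchanging the labels only if the source confirms it.
2. Check continuity at age 18 and state how subjects who change equation on study are handled.
3. State where measured TLC is collected, since the protocol's list of pulmonary function tests does not name it.
4. Re-derive % predicted TLC and the Table 5 category for affected adults at baseline, Month 12 and Month 24, and rerun the shift table.

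The cost is one corrected footnote, one derived variable and one rerun table. No new data are needed.
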